## Introduction

Despite current resuscitation practices, circulatory shock and perioperative organ injury after cardiac surgery occur in 25-40% of patients [1,2]. Traditionally, causes of shock after cardiovascular surgery with cardiopulmonary bypass are classified by macrocirculatory derangements (e.g. low cardiac output, vasoplegia, hypovolemia) [3]. Interventions to normalize hemodynamic variables, including mean arterial pressure, cardiac filling pressures, and cardiac output restore the large vessel (macrocirculatory) pressure and flow targets but may not reverse underrecognized disruptions in microcirculatory blood flow and oxygen utilization. Current methods to estimate the balance of oxygen delivery ( $DO_2$ ) relative to demand ( $VO_2$ ) include blood gas-derived calculations and the measurement of downstream biomarkers of anaerobic metabolism such as blood lactate. Using these methods, previous literature has concluded that lactic acidosis after cardiac surgery is unlikely related to inadequate oxygen delivery [4]. Unfortunately these inferences fail to consider the presence of regional blood flow derangements caused by pathologic microcirculatory heterogeneity, which are also associated with severity of postoperative lactic acidosis and organ injury [5,6]. To resolve this important clinical discrepancy, a deeper understanding of the determinants of oxygen transport pathways and oxygen utilization during health, shock, and resuscitation are needed.

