### Physiologic and pharmacologic data

Systemic hemodynamic data, perfusion data, and blood gas measurements will be collected upon ICU admission, then hourly during the first 6 hours of postoperative care. Cardiac output (CO), cardiac index (CI), central venous pressure (CVP), pulmonary artery pressure (PAP), and mixed venous oxygen saturation ( $SvO_2$ ) will be monitored continuously using a pulmonary artery catheter (Edwards Lifesciences LLC, Irvine, CA, USA). Arterial blood pressure will be measured using a standard invasive arterial line. Intraoperative and post-operative administration of blood products, intravenous fluids, vasoactive agents (vasopressor and inotropes), and sedatives will be recorded at each time point.

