#### Biological samples

Blood gas samples will be drawn into a commercial, pre-heparinized 1 mL blood sampler then immediately analyzed by an ABL90 FLEX automatic blood gas analyzer (Radiometer America Inc., Brea, California, USA). Arterial blood gas samples will be obtained by clinical staff every 1-2 hours for the first 6 hours after ICU admission based on current clinical practice. Central venous blood gas measurements will also be obtained by the study team at the time of microcirculation measurement. Hemoglobin, hematocrit, pH, PaO2, PaCO2, and glucose are also reported on each blood gas analysis. After 6 hours, blood gas analysis will be performed as needed by the clinical team. For biomarker and mitochondrial function analysis, enrolled patients will undergo phlebotomy with volumes of 15 mL drawn into K2EDTA tubes. Blood samples will then be centrifuged at room temperature using Ficoll-PaqueTM PLUS (GE) and Leucosep tubes (Greiner Bio-one). Plasma specimens will be stored at -80°C for later evaluation of the mechanisms of microcirculatory dysfunction. Peripheral blood mononuclear cells (PBMCs) will undergo further analysis and processing as detailed below.

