### Statistical and analysis plans

Continuous variables characterizing demographical data, microcirculation data, and mitochondrial respiration measurements, and outcomes data will be reported as means with standard deviations if normally distributed or medians with interquartile ranges if not normally distributed. Categorical variables will be represented as frequencies and proportions. To examine the predictive performance of selected variables for the primary outcome, we will construct receiver operator characteristic curves for threshold values of PVD, MHI, lactate,  $SvO_2$ , mean arterial pressure, and cardiac index. A Youden index will be calculated to determine the best cutoff value for determining prolonged VVFDs.

Linear regression modeling will be used to examine the relationship between L/P ratio and postoperative microcirculation variables. We will perform univariate analyses on candidate predictor variables of L/P ratio including PVD, MHI, LFTs, creatinine, CPB time, cross clamp time, and catecholamine administration. Multiple linear regression analysis will be used to model the effect of significant predictors. Repeated measure ANOVA will be used to compare changes in microcirculatory variables, mitochondrial respiration, and mitochondrial reactive oxygen species production over time. To adjust for multiple comparisons, post-hoc pairwise Tukey Kramer t-tests will be performed. All analyses will use statistical software (SAS version 15.1, Cary, NC; Prism v 9.0, Graph-Pad Software, San Diego, CA).

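### The exploratory L/P-ratio regression pre-specifies no measure of systemic oxygen delivery, so low flow or hemodilution could be read as a microcirculatory effect

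*Combined protocol and SAP*

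**What the plan says.** Under *Statistical and analysis plans*, the aim of the model is: "Linear regression modeling will be used to examine the relationship between L/P ratio and postoperative microcirculation variables". Univariate analyses come first, on "candidate predictor variables of L/P ratio including PVD, MHI, LFTs, creatinine, CPB time, cross clamp time, and catecholamine administration". The next step is: "Multiple linear regression analysis will be used to model the effect of significant predictors". Cardiac index and SvO2 appear in that section only among the variables for the ROC curves on the primary outcome.

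The systemic variables are collected. *Physiologic and pharmacologic data* has "Cardiac output (CO), cardiac index (CI), central venous pressure (CVP), pulmonary artery pressure (PAP), and mixed venous oxygen saturation" monitored continuously by pulmonary artery catheter, and states that hemodynamic, perfusion and blood gas data "will be collected upon ICU admission, then hourly during the first 6 hours of postoperative care". *Biological samples* lists "Hemoglobin, hematocrit, pH" and other values as reported on each blood gas, and adds a central venous gas drawn by the study team at each microcirculation measurement.

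The *Introduction* notes that "previous literature has concluded that lactic acidosis after cardiac surgery is unlikely related to inadequate oxygen delivery". It answers that such inferences overlook regional flow defects, and says the discrepancy needs resolving. *Outcome measures* places the relation of microcirculatory function to the L/P ratio among the exploratory outcomes.

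**The concern.** The Introduction contrasts two explanations of lactic acidosis after bypass: inadequate systemic delivery, and disturbed flow in small vessels despite adequate systemic delivery. A regression of L/P on PVD and MHI helps to separate them only if systemic delivery is held fixed.

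A common cause is plausible. Vessels count as perfused only if flow is scored sluggish or continuous, so low cardiac output could lower PVD directly. Hemodilution might do so too. Either could also raise L/P. These paths are physiological assumptions; the documents do not quantify them.

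If they operate, an L/P model without a delivery term gives PVD a coefficient even when PVD has no association of its own. The entry rule adds to this: a delivery variable added only as a candidate could fail the univariate screen and drop out.

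**Working it through.** **1. Candidates against data collected.** The plan gives no figure to reproduce here, so the first check compares lists.

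| Variable | Named L/P candidate | Collected |
|---|---|---|
| Cardiac output / cardiac index | No | Yes: continuous monitoring; hemodynamic data at ICU admission, then hourly for 6 h |
| Hemoglobin | No | Yes, on each blood gas |
| SvO2 | No | Yes, as for cardiac index |
| Arterial saturation | No | Not named; PaO2 is, so it may be derivable |
| Catecholamines, CPB time, cross clamp time | Yes | Yes |

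The catecholamine, CPB and cross clamp variables may partly track low flow or hemodilution, but they do not measure delivery.

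**2. Timing.** T2h images fall 0-2 hours after surgery and T4h images 2-4 hours after. Both lie in the period of hourly collection. T24h does not: hourly collection has ended and later arterial gases are drawn as clinically needed. Hemoglobin should still come from the study gas drawn with the image, but a complete delivery value at T24h is not assured.

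**3. Illustration of size.** Inputs: n = 134 (*Sample size and power*). Assumptions: correlation r between PVD and delivery; standardised effect of delivery on L/P of absolute size b; no PVD effect of its own; two-sided 5% test; L/P regressed on PVD alone.

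The PVD-L/P correlation is then r × b in absolute size. By Fisher's transformation, z = atanh(r × b) × √(134 − 3) = atanh(r × b) × 11.45, and the chance of a significant PVD coefficient is Φ(z − 1.96) + Φ(−z − 1.96).

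Example, r = 0.5 and b = 0.3: r × b = 0.15; atanh(0.15) = 0.1511; z = 1.73; Φ(−0.23) + Φ(−3.69) = 0.41.

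| b | r = 0.3 | r = 0.5 |
|---|---|---|
| 0.1 | 6% | 9% |
| 0.2 | 11% | 21% |
| 0.3 | 18% | 41% |
| 0.4 | 28% | 64% |

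Simulation (20,000 data sets per setting) agrees to within about one percentage point. With delivery in the model, the simulated rate was 4.5% to 5.2% throughout.

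**4. Effect of partial proxies.** At b = 0.3, adding one covariate correlated 0.5 with delivery (assumption) lowers 18-41% to about 13-27%. Adding two lowers it to about 10-20%. This requires that they survive the univariate screen.

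**5. Effect of the screen.** The plan states no screening level; take 5%. At b = 0.2, z = atanh(0.2) × 11.45 = 2.32, so delivery passes with probability Φ(0.36) = 0.64 and is dropped in about 36% of studies. Listing it as a candidate is therefore weaker than forcing it in.

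**The case against.** The case on the other side has five parts, and much of it stands.

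- **The analysis is exploratory.** This stands, and it sets the severity.
- **The list is open.** This also stands. A reader might infer that the model excludes systemic delivery; the wording leaves room to add it. What is missing is a commitment made before the results are seen.
- **The study's main comparison already includes global hemodynamics.** A reader might infer that the omission undermines the objective of outperforming global measurements. The documents do not support that. *Study objective* ties the aim to predicting clinical outcomes, and the corresponding ROC analysis includes lactate, SvO2, mean arterial pressure and cardiac index.
- **The illustration is not the planned model, and its inputs are assumed.** Correct. The plan is a multiple regression with possible proxies for delivery. The prior conclusion cited in the Introduction gives no support for a large delivery effect, and at b = 0.1 the excess over 5% is small.
- **Delivery may act through the microcirculation.** If so, adjustment removes part of a real pathway, and the unadjusted association still answers the literal aim of the model. This argues for reporting both estimates. The adjusted one is the contrast that the Introduction calls for.

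A reader might also take every component of oxygen delivery to be recorded at every image. The text does not go that far: arterial saturation is not named, and hourly collection stops at 6 hours.

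**Conclusion.** The point holds as a gap in pre-specification. No named L/P candidate measures systemic delivery, and the rule carrying only significant predictors forward would not guarantee a place for one that was added. As written, a significant PVD or MHI coefficient need not separate a microcirculatory association from low systemic delivery, which limits what the model can say about the Introduction's question. The primary VVFD comparison and the ROC analysis are untouched.

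The amount of bias is unknown. The 6% to 64% range rests on assumed correlations and a model containing PVD alone. It shows that the problem can be negligible or large, and should not be read as the expected error rate of the planned analysis. Confidence is high on the omission and low on its size. Severity: CONSIDER.

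**What to change.** Add to *Statistical and analysis plans* that, in the L/P model at the T2h and T4h images:

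- cardiac index and hemoglobin, time-matched to the image, enter the multiple regression whatever their univariate result;
- arterial saturation, or calculated oxygen delivery, is added where it is available or can be derived from the arterial gas;
- the PVD and MHI coefficients are reported with and without these terms, the adjusted ones being read as the association beyond systemic delivery, because delivery may act partly through the microcirculation.

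The cost is a short addition to the text and one or two extra model terms, a minor loss of degrees of freedom with about 134 subjects. Cardiac index and hemoglobin are already collected in this window, so no new procedure is needed.

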## **Sample size and power**

Using data from our previous foundational work as well as unpublished pilot data, we anticipate a 1:1 allocation of patients to the high ( $PVD > 22\text{mm/mm}^2$ ) and low group ( $PVD \leq 22\text{ mm/mm}^2$ ). We will need a sample size of at least 134 subjects to detect at least a 2-day difference in ventilator and vasopressor-free days (VVFDs) with a  $\beta=0.8$ , using a one-sided t-test  $\alpha=0.05$  [5,6]. We will enroll a total of 140 subjects to allow for a 5% loss to follow-up (surgical delay, ICU delay, cancelled surgery, etc.) and exclusion due inadequate microcirculation video quality (S1 Appendix).

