**Fig 3. Examples of VVFD scenarios to determine clinical outcomes.**

Exploratory outcomes will examine the relationship of microcirculatory function with common clinical biomarkers such as lactate,  $SvO_2$ , venous-to-arterial  $PCO_2$  gap, capillary refill time, and lactate to pyruvate ratio. Markers of endothelial injury and inflammation such as soluble vascular cell adhesion molecule 1 (sVCAM-1), soluble intercellular adhesion molecule 1 (sICAM-1), e-selectin, IL-8, IL-10, and other inflammatory cytokines will be measured. We will also examine mitochondrial complex function in human blood cells, comparing individual complex (I, II, III, and IV) function and reactive oxygen species generation between patients with and without post-operative shock.

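### The L/P-ratio regression admits only predictors that are significant one at a time, so PVD, MHI or their confounders can drop out and weak retained effects are overstated

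*Combined protocol and SAP*

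**What the plan says.** The Statistical and analysis plans section gives the aim: "Linear regression modeling will be used to examine the relationship between L/P ratio and postoperative microcirculation variables". Candidates are tested singly, and the text names "candidate predictor variables of L/P ratio including PVD, MHI, LFTs, creatinine, CPB time, cross clamp time, and catecholamine administration". The next sentence sets the rule for the joint model: "Multiple linear regression analysis will be used to model the effect of significant predictors". Read in order, significance refers to the one-at-a-time tests.

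The section states no p-value threshold, keeps no variable in regardless of its result, and describes no shrinkage, bootstrap or other allowance for selection. The Tukey-Kramer tests are described as post-hoc pairwise comparisons and do not bear on this model. It is the only multiple regression in the section.

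Under Outcome measures, the paragraph after the Fig 3 caption lists the L/P ratio as exploratory: "Exploratory outcomes will examine the relationship of microcirculatory function with common clinical biomarkers such as lactate". Sample size and power gives "We will need a sample size of at least 134 subjects to detect at least a 2-day difference" (in VVFDs) and "We will enroll a total of 140 subjects to allow for a 5% loss to follow-up". No sample size is given for the L/P model.

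**The concern.** The same data decide whether PVD and MHI appear in the joint model, which covariates adjust them, and what their coefficients are. Two things follow.

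- A weak predictor passes the screen mainly in samples where its estimate happens to be large, and ordinary intervals ignore this.
- A covariate related to both PVD and the L/P ratio can narrowly miss the cut-off and be dropped. A retained PVD then absorbs part of its effect.

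At stake are the size and precision reported for the link between microcirculation and L/P ratio. The Abstract expects the study to direct later research and therapeutic development, so those effect sizes may be reused.

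**Working it through.** **1. The plan's own figures.** The 134 belongs to the VVFD comparison. The available text gives no SD (it refers to S1 Appendix), so 134 cannot be reproduced independently. Solved backwards with 67 per group, a 2-day difference, one-sided alpha 0.05 and power 0.8: SD = 2 × √(67/2) / (1.645 + 0.842) ≈ 4.65 days. For attrition, 134/0.95 = 141.05, rounded up to 142, close to the planned 140. Here 134 serves only as the largest n that the plan treats as evaluable.

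**2. Room for the full model.** Seven named predictors: 134/7 = 19.1 subjects per coefficient, with 134 - 1 - 7 = 126 residual degrees of freedom. If LFTs and other items bring the count to ten: 134/10 = 13.4, with 123 degrees of freedom. Seven coefficients at ten subjects each need 70 subjects with an L/P value.

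**3. Mechanism, checked by hand.** Assume independent standardised predictors, residual SD 1, four true effects of 0.20, two of 0.10 and one of 0. The variance of the outcome is 1 + 4(0.04) + 2(0.01) = 1.18.
- True 0.10: univariate SE = √((1.18 - 0.01)/134) = 0.093. Passing at two-sided p<0.05 needs an absolute estimate above 1.98 × 0.0934 = 0.185, nearly twice the truth. The chance is P(Z > (0.185 - 0.10)/0.0934) = P(Z > 0.91) ≈ 18%.
- True 0.20: SE = √((1.18 - 0.04)/134) = 0.092, cut-off 0.183, chance ≈ 57%.

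**4. General simulation** (10,000 runs per scenario, n=134, univariate screen at p<0.05, then least squares on the survivors).

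| Scenario | Mean when retained | 95% interval coverage when retained |
|---|---|---|
| Independent, true 0.20 (kept in 57%) | 0.25 | 0.96 |
| Independent, true 0.10 (kept in 18-19%) | 0.21 | 0.86-0.87 |
| Independent, true 0 (kept in 5%) | about 0 | 0.33 |
| Correlated, true 0.20 | 0.20-0.23 (+2% to +14%) | 0.96-0.97 |
| Correlated, true 0.10 in the same mix | 0.165 (+65%) | 0.95 |
| Correlated, all true 0.10 | 0.13-0.18 (+30% to +80%) | 0.93-0.965 |

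The correlations assumed were CPB with cross clamp time 0.85, PVD with MHI 0.5, others 0.1. The full seven-predictor model returned the true values, with coverage 0.948-0.955 at n=134 and 0.946-0.956 at n=70.

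**5. PVD specifically** (4,000-5,000 runs, n=134; assumed correlations PVD-MHI -0.6, PVD-catecholamine -0.4, CPB-cross clamp 0.85, with the other correlations assumed separately in each set of runs).

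| True PVD effect (SD) | Other effects | Screen | Result when PVD is retained |
|---|---|---|---|
| 0 | modest CPB and catecholamine effects | p<0.05 | mean -0.10 to -0.11, coverage 84-90% |
| 0 | CPB and catecholamine 0.20 | p<0.05 | coverage 95% |
| -0.15 | none | p<0.05 | mean about -0.195 |
| -0.15 | none | p<0.20 | mean -0.152 |
| -0.15 | confounders also real | p<0.05 | mean -0.159 |
| -0.30 | CPB and catecholamine 0.20 | p<0.05 | mean -0.286 |

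Exaggeration in the third row: 0.195/0.15 = 1.30. In one null set with CPB and catecholamine effects of 0.15, PVD was kept in 22% of runs. In 36% of those, catecholamines or both bypass-time variables had been dropped. At n=70 the null case worsened to a mean of -0.16 with 76% coverage, while the full model stayed unbiased at about 95%.

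**6. Overall error rate.** In that null set at n=134, PVD was kept in 22% of runs with 89.5% coverage: 0.22 × (1 - 0.895) ≈ 0.023. Over all runs a false PVD finding therefore occurred in about 2.3%, against 5.0% for the full model.

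**7. Cost in precision.** Mean PVD interval width, full against screened: 0.472/0.414 = 1.14 with a null effect and 0.471/0.377 = 1.25 with a true -0.15. Across the simulations the increase was about 5-25%.

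**The case against.** The strongest reply is that the harm depends on the assumptions. The documents give no effect sizes, correlations or screening threshold. The plan's only stated alpha ("using a one-sided t-test" at 0.05) belongs to the VVFD sample size. A p<0.20 screen almost removes the exaggeration, and a strong PVD effect comes out slightly too small. This stands and limits the claim to weak effects under a strict screen.

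A reader might infer several stronger things that the documents do not support:

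- **That coverage is always too low.** With correlated predictors it was mostly near or slightly above 95%.
- **That false positives increase.** The low coverage is conditional on PVD being retained; over all runs the error rate was lower than with the full model.
- **That 134 subjects are assured for this model.** The number with an L/P value is not stated, and Biological samples describes no pyruvate measurement. The predictor list is open-ended and LFTs may be several variables, so 19 per coefficient is a best case.
- **That the plan promises an effect independent of all covariates.** It speaks only of a relationship and of candidate predictors. Creatinine, LFTs and catecholamine use may follow from poor microcirculation, and adjusting for them could remove part of the effect of interest.
- **That the change is free.** Intervals widen.

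Forcing in only PVD and MHI also restored about 95% coverage with negligible bias in simulation, so a lighter change would capture most of the gain. None of this defends a rule under which the variables being studied can be dropped by their own univariate p-values.

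**Conclusion.** The point holds in limited form. The selection rule is stated, it can discard PVD, MHI or their confounders, and a better rule uses the same data. For weak effects and an assumed two-sided p<0.05 screen at n=134, a retained PVD effect is overstated by about 30% (-0.15 becoming -0.195), or appears as about -0.10 when truly null, with 84-90% coverage. For strong effects or a looser screen the distortion is small or slightly reversed. The direction of the problem for weak predictors is secure; its size rests on assumed correlations and effects.

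Priority is low. The L/P analysis is exploratory, and the VVFD outcome, the secondary outcomes and the ROC analyses do not use this model.

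**What to change.** Replace the screening sentence with one prespecified multiple linear regression of L/P ratio that always contains PVD and MHI, plus a fixed set of the listed covariates chosen on subject-matter grounds and not by univariate p-value. State in advance:

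- whether CPB time, cross clamp time or both enter. At an assumed correlation of 0.85 the variance inflation factor is 1/(1 - 0.85²) = 3.6, which widens their intervals without biasing them;
- how LFTs are represented, and that the covariate list is closed;
- whether creatinine, LFTs and catecholamines, as possible consequences of poor microcirculation, belong in the main model or in a sensitivity model;
- how many subjects are expected to have an L/P value.

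Report the PVD and MHI coefficients with 95% confidence intervals and label the univariate results descriptive. If selection is kept for any other purpose, use penalisation or bootstrap the whole selection process.

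The change needs SAP wording only, with no new data. Its price is modestly wider intervals. Seven coefficients are comfortable at 134 subjects, and the full model stayed unbiased in simulation at 70.

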### **Methods and analysis**

This will be a prospective, observational study that includes patients undergoing elective cardiovascular surgery with cardiopulmonary bypass (CPB). Microcirculation will be quantified with sublingual incident dark field videomicroscopy. Mitochondrial respiration will be measured by performing a substrate-uncoupler-inhibitor titration protocol with high resolution respirometry on peripheral blood mononuclear cells at baseline and serial timepoints during resuscitation and at recovery as a possible liquid biomarker. Plasma samples will be preserved for future analysis to examine endothelial injury and other mechanisms of microcirculatory dysfunction. Thirty-day ventilator and vasopressor-free days (VVFDs) will be measured as a primary outcome, along with sequential organ failure assessment scores, and other clinical parameters to determine if changes in microcirculation and mitochondrial respiration are more strongly associated with clinical outcomes compared to traditional resuscitation targets.

This will be the first prospective study to examine both microcirculatory and mitochondrial function in human patients with circulatory shock undergoing cardiac bypass and address a key mechanistic knowledge gap in the cardiovascular literature. The results of this study will direct future research efforts and therapeutic development for patients with shock.

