### Incident Dark Field Microscopy

Sublingual microcirculation imaging will be performed using handheld incident dark field (IDF) videomicroscopy (CytoCam, Braedius Medical BV, the Netherlands) at four time points during the enrollment period. Imaging will be performed by the Principal Investigator or trained research personnel. Video sequences are obtained by placing the CytoCam device in the sublingual space and maneuvered so that pressure and motion do not result in image artifact (**Error! Reference source not found.**). A series of successive video clips (3-5 clips of at least 120 frames or 6 seconds in length) should be captured in distinct areas of the sublingual space to account for vessel heterogeneity. Focus and lighting during video capture may be adjusted to optimize image acquisition. Baseline ( $T_{0h}$ ) imaging will be obtained in the preoperative area prior to surgery on the day of the scheduled operation. Repeated measurements will be obtained upon arrival to the ICU (0-2 hours after surgery,  $T_{2h}$ ), during ongoing resuscitation (2-4 hours post-op,  $T_{4h}$ ), and on post-operative day one after recovery ( $T_{24h}$ ).

**Fig 2. A. Experimental setup with patient in supine position during IDF measurement. B. Anatomical sublingual triangle where measurements are obtained.**

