#### Analysis of IDF videomicroscopy

Prior to analysis, video quality will be assessed using the 6-factor Massey quality score, which uses a semiquantitative assessment of each video for appropriate illumination, duration, focus, content, stability, and pressure. Only videos with Massey scores of <10 will be included for further analysis [17]. Three videos with the best quality score will be selected for further processing. All IDF images will be coded then analyzed using an offline, dedicated software (Automated Vascular Analysis v3.02, Microvision Medical, The Netherlands). Microvascular flow index (MFI), microcirculatory heterogeneity index (MHI), total vessel density (TVD), proportion of perfused vessels (PPV), and perfused vessel density (PWD). Individual microvessel flow will be scored as 0=no flow, 1=intermittent flow, 2=sluggish flow, or 3=continuous flow. Vessels will be considered perfused if they are scored as either sluggish or continuous flow. To ensure only vessels contributing to tissue gas exchange and metabolism are included, only vessels < 20  $\mu$ m in diameter will be analyzed. This process follows the current standard for microcirculation measurement and analysis [18]. Interobserver variation will be tested periodically in at least 10% of the subject videos to ensure minimal scoring heterogeneity between investigators.

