### **Risk Assessment**

The risks for patients participating in this study are not greater than minimal risk and include those related to 1) blood collection for study measurements and 2) breach of confidentiality.

Since we will limit the volume of blood collection to less than 3 mL/kg or 50 mL and no more than two blood collections in one week, this falls under the provision of "not greater than minimal risk." For any patient whose clinical condition might be adversely affected by removal of the stated blood volume for this study (e.g., patients with significant anemia or compromised cardiac output), we will discuss further limiting the volume of blood withdrawn for research purposes with the patient's attending physician. Any patient concurrently enrolled in another study for who enrollment in this study would mean the combined blood volume collection would exceed IRB regulations will be excluded from participation in this study. Finally, since patients with shock typically undergo multiple blood draws per day and often have central and/or arterial vascular access devices, whenever possible blood sampling for study purposes will be timed with other clinically indicated blood draws or catheter access in order to limit pain from venopuncture, arterial puncture, and access to indwelling vascular catheters. Only caregivers with expertise and training in venopuncture, arterial puncture, or access of indwelling catheters will be permitted to collect blood specimens for this study.

In the rare cases where phlebotomy is performed for study purposes only, attempts will be made to mitigate patient discomfort by using topical anesthetics, such as EMLA. Also, risks will be minimized by limiting the number of attempts to obtain blood to 2 per patient per day and only individuals skilled at performing phlebotomy will be permitted to attempt.

To minimize a potential breach of patient confidentiality, CRFs will be coded with a study ID, all data will be password-protected, and the safeguards to ensure confidentiality as described.

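### Repeated-measures ANOVA is planned for all change-over-time analyses with no covariance structure or rule for missing time points; a likelihood-based mixed model on the same data is the better specification

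*Combined protocol and SAP*

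**What the plan says.** Statistical and analysis plans gives one method for change over time: "Repeated measure ANOVA will be used to compare changes in microcirculatory variables", mitochondrial respiration and mitochondrial ROS production. For multiplicity, "post-hoc pairwise Tukey Kramer t-tests will be performed". On implementation it says "All analyses will use statistical software" and lists SAS and Prism, without a procedure. The only missing-data rule in the document is the carry-forward rule for patients discharged early (Outcome measures), and it applies to VVFDs.

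Imaging is done "at four time points during the enrollment period" (Incident Dark Field Microscopy): T0h, T2h, T4h and T24h, with 3 to 5 clips each time. Under Analysis of IDF videomicroscopy, "Only videos with Massey scores of <10 will be included for further analysis", and the best three are analysed. No rule covers a time point at which fewer than three clips pass.

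Mitochondrial respiration is measured "at baseline and serial timepoints during resuscitation and at recovery" (Methods and analysis). The readable text gives no count of these samples, and Figure 1 is not shown.

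**The concern.** Three places in the protocol make gaps foreseeable. Poor clips are discarded, and a patient with the minimum of three clips has no spare. Sample size and power expects some exclusion for video quality. Risk Assessment allows research blood to be limited in significant anemia or compromised cardiac output, so some missing mitochondrial data may depend on the patient's condition.

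Classical repeated-measures ANOVA deletes a subject who lacks any one time point. That costs precision, and it can bias the estimated change when the gaps depend on earlier values. The univariate form also needs sphericity, meaning equal variances of all pairwise differences. T2h and T4h are about two hours apart in the same ICU phase, while T0h and T24h straddle the operation, so equal variances are unlikely.

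This is the only planned analysis of how the study's defining measurements change through surgery and resuscitation. As written, it permits two analyses, complete-case or all-available, that can give different answers.

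**Working it through.** **1. The plan's own figures.** There is none for this analysis. The nearest is the enrolment allowance in Sample size and power: 140 enrolled for 134 needed, so 6/140 = 4.3%, against a nominal 5% that covers loss to follow-up and poor video quality together. Spread independently over four time points, 5% overall means (1 − q)^4 = 0.95, so q = 1 − 0.95^(1/4) = 0.0127, about 1.3% per time point.

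**2. Complete subjects, imaging.** Four times and 140 subjects give 560 possible records. The rate q is an assumption. The complete share is (1 − q)^4, and an all-available analysis keeps 560 × (1 − q) records.

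| q per time point | (1 − q)^4 | Complete, of 140 | Records used, complete-case | Records used, all available |
|---|---|---|---|---|
| 1.3% | 0.95 | 133 | 532 | 553 |
| 5% | 0.815 | 114 | 456 | 532 |
| 10% | 0.656 | 92 | 367 | 504 |

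On a base of 134 the 5% and 10% rows become about 109 and 88. If gaps cluster in the same patients, more subjects are complete than shown.

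**3. Blood measures.** These figures do not carry over to mitochondrial respiration and ROS. Biological samples says "enrolled patients will undergo phlebotomy with volumes of 15 mL". Four such draws would be 4 × 15 = 60 mL, while Risk Assessment gives a 50 mL figure and "no more than two blood collections in one week". These passages and the serial sampling in Methods and analysis need to be reconciled. With only two samples the complete share would be 0.95^2 = 0.90 or 0.90^2 = 0.81, and sphericity would not arise.

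**4. Bias, by simulation.** All inputs are assumptions: 140 subjects, 1,000 runs, perfused vessel density (PVD) means of 25, 21, 21.5 and 23.5 mm/mm² at the four times, SD 3.5, correlation 0.5. Missing completely at random (MCAR) used 10% at each postoperative time. In the other scenarios T0h and T2h were always observed, and T4h and T24h were each missing with log-odds −2.1 + 1.2z. For missing at random (MAR), z is the T2h value in SD units below (or above) its mean. For missing not at random (MNAR), z is the same quantity below the mean for the affected visit's own value. About 102 of 140 subjects (73%) were complete. The true T2h-to-T24h change is 23.5 − 21 = 2.5. Simulation error on each bias is about 0.33/√1000 = 0.01.

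| Mechanism | Bias, complete-case | Bias, likelihood model |
|---|---|---|
| MCAR | −0.01 | −0.01 |
| MAR, low PVD missing | −0.48 | +0.01 |
| MAR, high PVD missing | +0.49 | +0.01 |
| MNAR, low PVD missing | +0.26 | +0.37 |

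Under MAR the complete-case error is about 0.48/2.5 = 19% of the true change, and its sign follows whichever patients go missing. In the low-PVD scenario the T0h and T2h means were biased by +0.47 and +0.96, so the true T0h-to-T2h fall of 4.0 appears as 4.0 − (0.96 − 0.47) = 3.51, although both values were observed for everyone. Deletion alone causes that error.

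Under MCAR the SD of the estimated T2h-to-T24h change was 0.346 (complete-case) against 0.311 (likelihood), a ratio of 1.11.

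Under MNAR the likelihood model had the smaller bias in the T24h mean (0.38 against 0.79), but the larger bias in the change, because the complete-case errors at T2h (0.53) and T24h partly cancel.

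The simulation used equal correlations, so it says nothing about the cost of violating sphericity.

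**The case against.** The strongest reply is that deletion of incomplete subjects is nowhere stated. Repeated-measures ANOVA is also a loose name for models fitted by likelihood, SAS can fit them, and Tukey-Kramer is the form that allows unequal numbers. This stands as far as it goes: complete-case analysis is inferred from the classical method. It does not settle the matter, because Tukey-Kramer adjusts contrasts and does not say how partial records enter the model.

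A reader might infer that one unusable image removes a subject. The documents do not support that: 3 to 5 clips are taken and three used, so one failed clip need not lose even the time point. Nor does intolerance of imaging create gaps as written, since Exclusion criteria removes such patients from the study. A cancelled operation leaves no postoperative data that any model could recover.

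A reader might also infer that the results would favour healthier patients. No section gives missingness by severity. The blood-limiting provision points that way for mitochondrial measures. For images the direction is unclear, because the only state-related example concerns non-intubated facemask patients.

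The 5% allowance is a fair counterweight: if all gaps stay inside it, about 133 of 140 subjects remain complete and the choice of method matters little. But that figure is an overall allowance and gives no rate per time point. The multivariate form of the ANOVA also avoids the sphericity assumption, though the plan does not say which form is meant.

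**Conclusion.** The point holds as a weakness in the named method and its specification. Gaps are foreseeable, nothing says how they are handled, and a better method is available with the same data and software.

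Its size depends on a missing rate the documents do not give. It is negligible near 1.3% per time point and material from about 5%, where 19% of subjects would be lost under independence (34% at 10%). Bias arises if missingness depends on observed earlier values, and its direction is not established.

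Two stronger conclusions should not be drawn. A mixed model does not remove bias in general: it does so under MAR, and in the MNAR scenario its error in the T2h-to-T24h change exceeded that of complete-case analysis. Nor does the point reach the primary VVFD comparison, the ROC analyses or the 134/140 sample size, none of which uses the repeated-measures model. Change over time is not a listed primary or secondary outcome.

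**What to change.** Replace the repeated-measures ANOVA sentence with a linear mixed model for repeated measures: time as a categorical fixed effect, unstructured covariance across times, REML with Kenward-Roger degrees of freedom, and all available observations. Take the pairwise time contrasts from this model with Tukey-Kramer adjustment. For the planned mitochondrial comparison between patients with and without postoperative shock (Outcome measures), which has no stated model, add shock status and shock-by-time.

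Alongside this:

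- State when an imaging time point counts as missing, including when fewer than three clips pass.
- Report missingness by time point and reason, separately for images and blood.
- Add a simple MNAR sensitivity analysis, for example shifting the unobserved postoperative values by a range of fixed amounts.
- Reconcile the blood-sampling passages so that the number of mitochondrial time points is known before the model is fixed.

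The cost is a paragraph of SAP text and slightly more analysis work. Data collection, software and sample size do not change.
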